5.4 Handling of Missing or Incomplete Dates

Unless otherwise specified, missing data will not be imputed for the analyses.

Medications with partial or missing dates will be imputed as follows:

- **Missing or partial medication start date:**
 - If only DAY is missing, the first day of the month will be assumed.
 - If DAY and Month are both missing, the first day of the year will be assumed.
 - If DAY, Month and Year are all missing, the date before the first dose date (Day 1) will be assumed.
- **Missing or partial medication stop date:**
 - If only DAY is missing, the last day of the month will be assumed.
 - If DAY and Month are both missing, the last day of the year will be assumed.

-
- c. If DAY, Month and year are all missing, 'ongoing' status to stop date will be assigned.

AEs with missing or incomplete onset dates will be counted as treatment emergent unless the event has a complete end date that occurs prior to the first vaccination dose OR month and year of AE onset or stop date indicate the AE occurs prior to the first vaccination dose.

Imputation rules for missing or partial AE start date are defined below:

If only day of AE start date is missing:

- If the AE start year and month are the same as that for the first dose date, and if the full (or partial) AE end date is not before the first dose date or AE end date is missing, then impute the AE start day as the day of first dose date;
- Otherwise, impute the AE start day as 15 of the month and compare with the AE end date if not missing. If the AE end date is before the imputed AE start date, set AE start date to AE end date.

If Day and Month of AE start date are missing:

- If AE start year = first dose year, and if the full (or partial) AE end date is not before the first dose date or AE end date is missing, then impute the AE start month and day as the month and day of first dose date;
- Otherwise, impute the AE start month as July and the day as 1 and compare with the AE end date if not missing. If the AE end date is before the imputed AE start date, set AE start date to AE end date.

There will be no imputation for completely missing or partial AE end dates. If the start date is completely missing for an AE, the AE is considered to be treatment-emergent unless the collection date is prior to the treatment start date.

5.5 DSMB Stopping Rules

5.5.1 Individual Level Rules

Stopping rules are proposed as conditions that would stop further vaccinations in an individual subject (at any dose level) if they experience any of the following events that are assessed as possibly related by the investigator, or for which there is no alternative, plausible, attributable cause:

- Fever $>40.0^{\circ}\text{C}$ ($>104.0^{\circ}\text{F}$) for at least 1 daily measurement within 7 days after vaccination,
- Any grade 4 or life-threatening event within 7 days after any study injection, regardless of relationship to study vaccine,
- Clinically significant systemic reaction (i.e., angioedema, generalized urticaria) within 7 days after any study injection,
- SAE that is assessed by the investigator as possibly related, or for which there is no alternative, plausible, attributable cause.

Safety data will be monitored on an ongoing basis by the site investigators and sponsor in order to promptly identify and flag any event that potentially contributes to a stopping rule. If the DSMB recommends unblinding of individual cases, data from placebo recipients will not contribute to the stopping rules.

5.5.2 Trial Level Rules

Study randomization and further vaccinations will stop if 2 or more participants receiving VBI-2902a meet stopping rules unless the DSMB and study sponsor and site investigators review the safety data, and in consultation with BRDD, determine that safety of study participants is not affected and that study vaccination may continue.

If any of these safety signals are met at any point during the study, the result of the discussions by the DSMB will be communicated by the Sponsor designate to the study centers and the regulatory authorities.

An investigator who identifies any safety concern (i.e., meeting of stopping rules or any other safety concern) should inform the Medical Director at the study CRO immediately, and further enrollment may be put on hold as a consequence.

Of note, no formal stopping rule will be applied for other safety data such as missed visits due to product-related AEs, Grade 2 AEs and AEs collected from Day 7 to Day 29 after injection. However, the DSMB will review these data, if available, in order to allow for an overall assessment of the benefit to risk.

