	
Stopping rules - study vaccinations will stop if 2 or more participants receiving VBI-2902a or VBI-2905a meet stopping rules criteria unless the DSMB and study sponsor and site investigators review the safety data, and in consultation with BRDD, determine that safety of study participants is not affected and that study vaccination may continue.
 
Immunogenicity criteria for study continuation
 
Neutralizing antibody (nAb) titers, determined by pseudovirus microneutralization assay and plaque-reduction neutralization test (PRNT) on serum collected at Day 28 (4 weeks after the first vaccination) and Day 56 (4 weeks after the second vaccination) will be used as the primary determinant for immunogenicity, and will determine whether the study will proceed to Phase 1b. Additional immunological endpoints, described below, will also be considered as secondary endpoints.
 
Geometric mean nAb titers and binding antibodies to spike protein and its receptor binding domain (RBD) in one-dose and two-dose groups in Phase 1a at Days 1, 7, 28, 35 and 56 will be compared against a panel of COVID-19 convalescent sera as well as a WHO International Standard of high titer pooled COVID-19 convalescent sera. A non-inferior GMT nAb titer against the GMT of the panel of COVID-19 convalescent sera (tested against the original Wuhan strain PNA for phase 1a participants and against the B.1.351 variant PNA in phase 1b) in subjects receiving 2 doses of VBI-2902a will justify proceeding to Phase 1b; comparison of the nAb GMT against the WHO reference standard will be used to aid benchmarking against other COVID-19 vaccine candidates. Day 28 antibodies to RBD and T-cell endpoints will be considered if Day 56 nAb results do not allow a clear determination of equivalence or superiority to the convalescent sera neutralizing antibody GMTs. If responses are inferior to that of the panel of convalescent serum, neither VBI-2902a nor VBI-2905a will undergo further testing at the proposed dose levels and dose regimens. In Phase 1b the percentage with a 4- fold or greater increase in nAb titers following vaccination will be determined, as this represents a meaningful boosting of immunity.
 
The group sizes will allow determination of at least two-fold differences in nAb titers at a power of 80% with an alpha error of 0.05. Safety and tolerability will be evaluated in the total of ~67 participants who will receive at least one dose of VBI2902a or VBI- 2905a and in ~47 participants who will receive placebo. If no safety signals are detected and immunogenicity is demonstrated, further clinical development will be considered.
 
Further clinical development may not be considered if nAb titers are not equivalent to or superior to that of the panel of COVID-19 convalescent serum. The safety, tolerability and percentage of subjects with 4-fold or greater increases in neutralizing antibody titers at Days 28 and 56 will be used to determine whether further clinical development of a one-dose vaccination regimen is justified.

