--	---

	
stopping rule. If DSMB recommend unblinding of individual cases, data from placebo recipients will not contribute to the stopping rules. Study randomization and further vaccinations of all participants will stop if 2 or more participants receiving VBI-2902a or VBI-2905a meet stopping rules criteria unless the DSMB and study sponsor and site investigators review the safety data, and in consultation with BRDD, determine that safety of study participants is not affected and that study vaccination may continue.
 
Surveillance of events that could represent enhanced COVID-19 Study participants will be tested (SARS-CoV-2 PCR or rapid antigen test) and surveyed for potential COVID-19 illness throughout the study. All confirmed cases will be reviewed contemporaneously by Medical Monitor, DSMB and the study sponsor.
 
Pregnancy Testing For female participants of child-bearing potential, pregnancy testing will be performed immediately before each vaccination. A negative pregnancy test result will be required prior to the study vaccination.
 
Follow-up Duration Participants will be followed a minimum of 12 months (assuming 28 days per month) after the Day 1 immunization with at least six-month follow-up safety assessments after last dose.

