4.4 Early DSMB Study Review and Continuation Criteria

Safety criteria for study continuation

Early DSMB reviews of post-vaccination safety data and stopping rules will be implemented for safety and protection of study participants (see [Section 5.2, Protection of Participants](#), below).

In Phase 1a, the second vaccination will proceed only after the DSMB has confirmed that the vaccine safety and tolerability is acceptable and that stopping rules were not met through 7 days after the first dose.

In Phase 1b, DSMB will review blinded Day 7 safety data after the first 10 participants in each group. Only after the DSMB confirms that safety is acceptable and that stopping rules were not met will the enrollment in the respective study groups continue to its completion.

For details on timing of DSMB reviews, please see [Figure 1](#) above.

Stopping rules

Study vaccinations will stop if 2 or more participants receiving VBI-2902a or VBI-2905a meet the stopping rules criteria (defined in [Section 10.7](#)) unless the DSMB and study sponsor and site investigators review the safety data, and in consultation with the appropriate regulatory authorities, determine that the safety of study participants is not affected and that study vaccination may continue.

Immunogenicity criteria for study continuation

Neutralizing antibody (nAb) titers, determined by pseudovirus microneutralization assay and plaque- reduction neutralization test (PRNT) on serum collected at Day 28 (4 weeks after the first vaccination) and Day 56 (4 weeks after the second vaccination) will be used as the primary determinant for immunogenicity. Additional immunological endpoints, described below, will also be considered as secondary endpoints.

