Geometric mean titers (GMT) of nAb and binding antibodies to the spike protein and its receptor binding domain (RBD) in one-dose and two-dose groups in Phase 1a at Days 1, 7, 28, 35 and 56 will be compared against a panel of COVID-19 convalescent sera as well as a WHO International Standard of high titer pooled COVID-19 convalescent sera. Day 28 antibodies to RBD and T-cell endpoints will be considered if Day 56 nAb results do not allow a clear determination of equivalence or superiority. If responses are inferior to that of the panel of convalescent serum in Phase 1a and Phase 1b, neither VBI-2902a nor VBI-2905a will undergo further testing at the proposed dose levels and dose regimens. In Phase 1b, the percentage of subjects with a 4-fold or greater increase in nAb titers will be determined, as this represents a meaningful boosting of immunity.

The group sizes will allow determination of at least two-fold differences in nAb titers at a power of 80% with an alpha error of 0.05. Safety and tolerability will be evaluated in the total of ~67 participants who will receive at least one dose of VBI-2902a or VBI-2905a and in ~47 participants who will receive placebo. If no safety signals are detected and immunogenicity is demonstrated, further clinical development will be considered. Further clinical development may not be considered if optimal nAb titers are not equivalent to or superior to that of the panel of COVID- 19 convalescent serum. The safety, tolerability and percentage of subjects with 4-fold or greater increases in nAb titers at Days 28 and 56 will be used to determine whether further clinical development of a one-dose vaccination regimen is justified.

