10.7 Safety Monitoring and Study Stopping Rules

Stopping rules are proposed as conditions that would stop further vaccinations in an individual subject (at any dose level) if they experience any of the following events that are assessed as possibly related by the investigator, or for which there is no alternative, plausible, attributable cause:

- Fever >40.0°C (>104.0°F) for at least 1 daily measurement within 7 days after vaccination
- Any grade 4 or life-threatening event within 7 days after any study injection, regardless of relationship to study vaccine
- Clinically significant systemic reaction (i.e., angioedema, generalized urticaria) within 7 days after any study injection
- SAE that is assessed by the investigator as possibly related, or for which there is no alternative, plausible, attributable cause

Safety data will be monitored on an ongoing basis by the site investigators and sponsor in order to promptly identify and flag any event that potentially contributes to a stopping rule. If the DSMB recommends unblinding of individual cases, data from placebo recipients will not contribute to the stopping rules.

Study randomization and further vaccinations will stop if 2 or more participants receiving VBI-2902a or VBI-2905a meet stopping rules unless the DSMB and study sponsor and site investigators review the safety data, and in consultation with the appropriate regulatory authorities, determine that safety of study participants is not affected and that study vaccination may continue.

If any of these safety signals are met at any point during the study, the result of the discussions by the DSMB will be communicated by the Sponsor designate to the study centers and the regulatory authorities.

An investigator who identifies any safety concern (i.e., meeting of stopping rules or any other safety concern) should inform the Medical Director at the study CRO immediately, and further enrollment may be put on hold as a consequence.

Of note, no formal stopping rule will be applied for other safety data such as missed visits due to product-related AEs, Grade 2 AEs and AEs collected from Day 7 to Day 29 after injection. However, the

DSMB will review these data, if available, in order to allow for an overall assessment of the benefit to risk.

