1 INTRODUCTION

The purpose of this Statistical Analysis Plan (SAP) is to provide detailed descriptions of the statistical methods, data derivations and data displays for study protocol VBI-2902a-CT01, “A Phase 1a/1b Study to Evaluate the Safety, Tolerability, and Immunogenicity of the COVID-19 (SARS-CoV-2) Vaccine Candidates VBI-2902a and VBI-2905a in Healthy Adults”, Version 6.0 dated 20 May 2022. The table of contents and templates for the Tables, Figures and Listings (TFLs) will be produced in a separate document.

The preparation of this SAP has been based on International Conference on Harmonisation (ICH) E3 and E9 guidelines.

All data analyses and generation of TFLs will be performed using SAS 9.3® or higher.

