3 STUDY DESIGN

Overview

The trial will be a phase 1a/1b study, randomized, observer-blind, placebo-controlled.

Description of study parts and groups

Phase 1a

Phase 1a of the study will evaluate the safety, tolerability and immunogenicity of a one-dose or two-dose regimen of the VBI-2902a at the low dose level of 5 µg of S protein or placebo in 60 healthy adults 18 to 54 years of age with no previous clinical or laboratory diagnosis of COVID-19 or SARS-CoV-2 infection and not previously received an experimental or authorized COVID-19 vaccine. Participants will be randomized to three cohorts at a 1:1:1 ratio (2:1 ratio to VBI-2902a or placebo [saline]):

- **Group G1** – 20 participants will receive VBI-2902a at a dose of 5 µg of S protein at Day 1 and placebo at Day 28.

- **Group G2** – 20 participants will receive VBI-2902a at a dose of 5 µg of S protein at Days 1 and 28.
- **Group G3** – 20 participants will receive placebo at Days 1 and 28.

An Independent Data Safety Monitoring Board (DSMB) will review blinded safety data (reactogenicity, adverse events and safety laboratory assessments) at Day 7 after the first vaccination. The second vaccination will only be given if the DSMB confirms that Day 7 safety is acceptable and that stopping rules were not met. The DSMB will further review blinded post-vaccination safety through Day 35, 7 days after the second vaccination and through Day 56, 28 days after the second vaccination. A Study Steering Committee (SSC), comprised of representatives from the study sponsor (not involved in study operations) and external vaccine experts, will review unblinded immunogenicity data 7 days and 28 days after the second vaccination. The study will be unblinded following DSMB review of safety data collected through Day 56.

Phase 1b

Phase 1b of the study will evaluate the safety, tolerability and immunogenicity of a one-dose regimen of VBI-2905a at a 5 µg dose level of S protein in healthy adults (18-54 years) who had been previously vaccinated with mRNA vaccines.

The DSMB will perform an early review of blinded post-vaccination safety data at Day 7 (reactogenicity, AEs and safety laboratory assessments). DSMB will review blinded Day 7 safety data after the first 10 participants in groups G4 and G5 (previously vaccinated). Only after the DSMB confirms that safety is acceptable and that stopping rules were not met will the enrollment in the respective study groups continue to its completion.

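### SAP 5.5.2 words the trial-level stopping rule for VBI-2902a only, omitting all 27 planned VBI-2905a recipients whom the protocol's rule counts

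*SAP*

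**What the plan says.** The SAP covers both products: its Introduction names the "Vaccine Candidates VBI-2902a and VBI-2905a in Healthy Adults" and ties the plan to protocol Version 6.0. SAP 3 says "Phase 1b of the study will evaluate the safety, tolerability and immunogenicity of a one-dose regimen of VBI-2905a", and the only other arm in that phase is placebo. SAP 3 also lets Phase 1b enrolment run to completion only once the DSMB has confirmed, after a first look at Day 7 data, that the stopping rules have not been met.

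The trial-level rule in SAP 5.5.2 reads "Study randomization and further vaccinations will stop if 2 or more participants receiving VBI-2902a meet stopping rules". Protocol 10.7 reads "Study randomization and further vaccinations will stop if 2 or more participants receiving VBI-2902a or VBI-2905a meet stopping rules". Apart from that product list and the regulator to be consulted, the two sentences are near-identical.

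On blinding, SAP 5.1 says that the DSMB sees blinded safety displays in both phases, with individual unblinding at its request. The same paragraph then says, with no time point or condition, that the DSMB sees unblinded displays during Phase 1b. It refers the details to the DSMB SAP.

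**The concern.** Two current documents state one safety rule differently, and the SAP's version leaves out the product given in Phase 1b. Anyone applying SAP 5.5.2 to the Phase 1b enrolment check in SAP 3 would find a count to which no VBI-2905a recipient can add. At stake is whether two qualifying events on VBI-2905a stop dosing by default or only by discretion.

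The SAP 5.1 contradiction matters less. It leaves a reader unsure whether the Phase 1b displays prepared for the DSMB before the Day 56 unblinding should be blinded.

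**Working it through.** **Inputs.** Planned group sizes are in Protocol 4.1 and Table 3: G1 = 20 and G2 = 20 on VBI-2902a, G4 = 27 on VBI-2905a, G3 = 20 and G5 = 27 on placebo.

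**Step 1: reproduce the protocol's figure.** Protocol 4.4 says "Safety and tolerability will be evaluated in the total of ~67 participants who will receive at least one dose of VBI-2902a or VBI-2905a". Active recipients: 20 + 20 + 27 = 67, which agrees. Placebo: 20 + 27 = 47, also as stated. Total: 67 + 47 = 114, matching Table 3.

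**Step 2: compare the statements of the rule.**

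| Place | Wording | Counts VBI-2905a? |
|---|---|---|
| Protocol synopsis, Study Continuation Criteria | "study vaccinations will stop if 2 or more participants receiving VBI-2902a or VBI-2905a meet stopping rules criteria" | Yes |
| Protocol synopsis, Stopping Rules | "receiving VBI-2902a or VBI-2905a meet stopping rules criteria unless the DSMB and study sponsor and site investigators review the safety data" | Yes |
| Protocol 4.4 | "Study vaccinations will stop if 2 or more participants receiving VBI-2902a or VBI-2905a meet the stopping rules criteria" | Yes |
| Protocol 10.7 | "Study randomization and further vaccinations will stop if 2 or more participants receiving VBI-2902a or VBI-2905a meet stopping rules" | Yes |
| SAP 5.5.2 | "Study randomization and further vaccinations will stop if 2 or more participants receiving VBI-2902a meet stopping rules" | No |

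All four protocol statements name VBI-2905a; the single SAP statement does not.

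**Step 3: who is counted under the SAP wording.**
- Counted: 20 + 20 = 40, and 40/67 = 59.7%.
- Left out: 27, and 27/67 = 40.3%.
- Within Phase 1b: 0 of 27 active recipients.

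**Step 4: does another rule in SAP 5.5 fill the gap?** The individual-level criteria in SAP 5.5.1 name no product, so they apply to VBI-2905a recipients. Their stated consequence, however, is to stop that person's later injections, and Phase 1b gives a single dose. The count in SAP 5.5.2 is therefore the only numeric rule in SAP 5.5 that can halt dosing of the Phase 1b participants still to come. SAP 5.5.2 also allows enrolment to be held when an investigator raises a safety concern, but that hold is optional.

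**Step 5: DSMB blinding in Phase 1b.**
- Blinded: the earlier sentence in SAP 5.1; SAP 3 for the Day 7 review; and the protocol in its synopsis (Study Design), 4.8, 5.2 and 10.7.1. The last of these allows unblinding at the DSMB's request.
- Unblinded without limit: one sentence in SAP 5.1.
- General unblinding of each phase comes only after the Day 56 review (Protocol 4.1 and 8.7.1, SAP 7).

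The SAP 5.1 sentence stands alone against its own paragraph, its own Section 3 and the protocol.

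**The case against.** The strongest reply is that little turns on this. Stopping dosing is a matter of trial conduct, and Protocol 11.4 points to Protocol 10.7 for it, where the rule is complete. SAP 2 limits the SAP to the final and Study Steering Committee assessments and mentions a separate DSMB SAP. SAP 7 declares no change from the protocol's analyses and refers to DSMB judgement of the safety of both products. A DSMB could also treat a VBI-2905a recipient who meets the product-neutral criteria in SAP 5.5.1 as a stopping rule met. All of this stands, and it lowers the practical weight. It does not make SAP 5.5.2 correct: that section is headed as the DSMB's stopping rules and states the rule in full.

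A reader might infer more than the documents support:

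- *That Phase 1b had no stopping rule.* The protocol rule covers VBI-2905a throughout.
- *That someone chose to exclude VBI-2905a.* Nothing points to a choice. SAP 7 points the other way, and SAP 6.4.1 carries similar stale text on a 10 µg dose group that is not in the current design.
- *That 40 against 67 measures a change in the chance of stopping.* It is a head count. Phase 1b starts only after Phase 1a safety through Day 56 is cleared (Protocol 4.8 and 10.7.1.1), so the two products are not at risk together. The documents give no event rate from which a trigger probability could be taken.
- *That the DSMB actually worked unblinded in Phase 1b, or was meant to after Day 56.* The first cannot be known from these documents. For the second, no document provides for routine unblinded DSMB review at that stage; Protocol 10.7.1 says blinded, with unblinding on request. The stray sentence may be left over from the open-label group G6 removed in Version 6.0, but that is a guess.

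**Conclusion.** The point holds as a cross-document inconsistency: SAP 5.5.2 is wrong as written. Taken literally it counts 40 of 67 planned active recipients and 0 of 27 in Phase 1b, where the protocol counts all of them. The SAP 5.1 contradiction is also real, but secondary.

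No endpoint estimate, test or safety tabulation changes. The conclusion rests on planned group sizes and a literal reading of the SAP. Two unknowns limit its practical effect. The DSMB SAP was not available and may state both matters correctly. The documents also do not say whether Phase 1b dosing was still under way at the SAP's date (05 October 2022). If dosing was over, the effect on conduct is smaller, but the SAP still misstates the rule that applied. It should be corrected because it concerns a safety rule and costs almost nothing to put right.

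**What to change.** 1. In SAP 5.5.2, insert *or VBI-2905a* after *VBI-2902a* in the first sentence and leave the rest unchanged.
2. In SAP 5.1, delete the sentence that has the DSMB reviewing unblinded data during Phase 1b. What remains is blinded review with unblinding at the DSMB's request, as in Protocol 10.7.1. Do not draft a new provision for unblinded review after Day 56.
3. Check both wordings in the separate DSMB SAP. At the same time, confirm how the SAP 5.1 statement that DSMB outputs are shown by actual treatment fits with blinded displays, since the deletion alone does not settle that.

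The cost is two added words, one deleted sentence and a check of one companion document. No protocol text, participants, procedures or analyses change.
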